As for other bacterial and viral pneumonia, several scores defining an outpatient setting are successfully used; we choose to adapt the CURB-65³ score in the context of SARS-CoV-2 pneumonia. The algorithm included a medical evaluation and paraclinical tests at baseline to ensure the absence of hospitalization criteria⁴ (pneumonia with CURB-65 ≥ 2 or new O₂ dependency or increased O₂ requirements or sustained respiratory rate ≥20 min or decompensated comorbidity or major alteration of the general state). We also took into account the social situation of patients in order to ensure effective isolation measures and support at home. If the management chosen was to keep the patient in an outpatient setting, a follow-up was organised (figure 1): follow-up could be done by phone or by the patient's primary care physician or by an outpatient general medicine consultation at the HUG. For on-site visits, a specific track was established to avoid contact with other patients or healthcare workers

The purpose of this study is to evaluate our strategy for outpatients SARS-CoV-2 moderate pneumonia management in terms of efficacy and patient safety. Our ultimate goal is to validate our first wave management strategy in order to support our future approach in the event of a second wave, and spare the hospital resources by safely keeping at home as many patients as possible.

Version du 02.04.2020 – Groupe Guidelines Covid-1

Figure 1: Moderate pneumonia outpatient management algorithm⁵

2. Objective

Validation of our strategy in terms of safety and efficacy for the treatment of moderate SARS-CoV-2 pneumonia

3. Origin of data and material

We focused on patients consulting in the emergency department at the HUG who remained in an outpatient setting, with pneumonia and moderate illness, defined by individuals who have evidence of lower respiratory disease by clinical assessment or imaging and a saturation of oxygen (SaO₂) $>$ 93% on room air and no other hospitalization criteria (CURB 65 score below 2points).

For patients' follow-up, we have created an aftercare ambulatory unit, open 5/7 days. We were able to conduct 64 consultations between April 2 and May 5, 2020. Every patients had suspected or confirmed SARS-CoV-2 pulmonary tract infection.

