The follow-up data was entered into DPI (patient's medical record at HUG) on a specific consultation form. Patients followed in our consultation were contacted between 30 and 60 days after diagnosis by the Covicare team. The Covicare team is call-center composed of medical students and primary care physicians who remotely followed patients with COVID-19 by calling them by phone or telemedicine every day or every other day depending on patients' needs and health status. We will export data from RedCap concerning post-hospitalization, satisfaction survey on our care and oral consent for use of data (ARGOS study CCER number 2020-01273). We will coordinate with the unified HUG database, which is in process by [name].

4. Inclusion Criterias

All persons with suspected or confirmed SARS-CoV-2 pneumonia who consulted in the emergency department of the HUG without criteria for hospitalization⁴ (Pneumonia with CURB-65 ≥ 2 or new O₂ dependency or increased O₂ requirements or sustained respiratory rate ≥ 20 min or decompensated comorbidity or major alteration of the general state) and who have been scheduled for outpatient follow-up in HUG.

5. Exclusion Criterias

Patients with hospitalization criteria⁴

Refusal to consent documentation found in the computerized patient record or oral refusal consent during follow up call.

6. Information and consent of participants

All data are from our daily clinical activity with patients with SARS-CoV-2 pneumonia who visited the Ambulatory Care Unit between April 2, 2020 and May 5, 2020. The Covicare team obtained their consent by telephone for the use of the data at the time of diagnosis. A form was sent to them by message to validate their consent in writing (see attached file name "Consentement à l'utilisation des données en lien avec le COVID19 à des fins de recherche".) Moreover, since the beginning of the outbreak, the HUG screening and emergency sites contain an informative poster mentioning that patient clinical data can be used and collected in clinical studies on COVID-19. Any patient who refuses to allow their data to be used must inform the health care provider at the time of care, and this refusal is insert into DPI. Such patients will be excluded from the study.

7. Scientific methodology

We want to elaborate a retrospective and prospective cohort study.

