The statistical analyses will be descriptive only. Given the small sample size of patients, no statistical measures of association will be performed. The data collection period is from April 2 to May 5, 2020. The satisfaction study will be prospective, within the 3 months after diagnosis.

The primary outcome will be secondary hospitalization(s) or death COVID-19 related, until 30 to 60 days from diagnosis

Secondary outcomes will be

- number of unexpected COVID-19 related outpatient visits until day 30 to 60 from diagnosis,
- severity of COVID-19 disease on a 7-points ordinal scale at 30 to 60 days after diagnosis of SARS-CoV-2 (1: not hospitalized, no limitation of activities; 2: not hospitalized, limitation of activities; 3: hospitalized, not requiring supplementary oxygen; 4: hospitalized, requiring supplementary oxygen; 5: hospitalized, on non-invasive mechanical ventilation; 6: hospitalized, on invasive mechanical ventilation or ECMO; 7: death),
- patient satisfaction with management strategies
- estimation of saved costs compared with a strategy of hospitalization of all COVID-19 related pneumonia cases.

8. Obligation to announce

A change in the study's orientation or of the elements mentioned in the decision must be announced beforehand to the competent ethics committee.

9. Data protection: coding and preservation

Removing direct and indirect identifiers will coded data extracted from the DPI. Record ID will be created using a number (1 to 100 for example). This record ID will be reported on the paper survey filled by physicians. Anonymized data will be stored in Microsoft Excel format, protected with a password and on a HUG server, on the responsibility of [name] [name].

10. Procedure concerning non coded data

Data from the physician survey will be coded by [name] [name] and matched with coded data using the record ID. Coded data will be stored in Excel format, protected with a password and on a HUG server, on the responsibility of [name] [name].

11. Data storage

Anonymized coded data will be stored in Excel format, protected with a password and on a HUG server, on the responsibility of [name] [name].

Only [name] [name] can modify the protected Excel file. At each modification, a PDF extract will be made, and named after the date and the initials of the contributor. Paper surveys will be stored in a locked drawer in [name] [name] HUG office.

12. Storage time

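### Section 4 builds the cohort from patients scheduled for HUG follow-up, Section 6 from patients who visited the unit; if Section 6 is followed, the primary outcome omits scheduled patients who never attended

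*Protocol*

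**What the plan says.** - **Section 4 (inclusion).** The cohort is all persons with suspected or confirmed pneumonia seen in the HUG emergency department, without hospitalisation criteria, "who have been scheduled for outpatient follow-up in HUG". Attendance is not a condition. Section 5 excludes patients with hospitalisation criteria and those who refuse consent; it does not exclude non-attenders.
- **Section 6 (information and consent).** "All data are from our daily clinical activity with patients with SARS-CoV-2 pneumonia who visited the Ambulatory Care Unit", with the visit dated between April 2 and May 5, 2020.
- **Section 3 (origin of data).** It opens with emergency patients who stayed outpatients, but the data it then describes are tied to the consultation. There were 64 consultations between April 2 and May 5, follow-up data were entered "on a specific consultation form", and the late contact is described as "Patients followed in our consultation were contacted between 30 and 60 days after diagnosis by the Covicare team". On the unit itself: "we have created an aftercare ambulatory unit, open 5/7 days".
- **Section 7 (methodology).** "The primary outcome will be secondary hospitalization(s) or death COVID-19 related, until 30 to 60 days from diagnosis". The same dates return as "The data collection period is from April 2 to May 5, 2020", without saying whether they date the emergency attendance, the diagnosis or the unit visit.

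**The concern.** Scheduled and visited are two entry conditions, and they separate exactly where it matters for a safety estimate. The study is meant to validate keeping patients at home, a decision taken at the emergency attendance. The risk period for the primary outcome starts at diagnosis. If entry depends on a later visit, a patient whose home management failed early and who never reached the unit is absent from the result, although Section 4 counts that patient as included and the primary outcome counts the admission or death as an event.

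The analysis is descriptive, so the main result is essentially one numerator over one denominator, in a small group. Two readers applying the two sections could obtain different values for both.

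**Working it through.** The protocol gives no event rate or patient count to reproduce. The check is a comparison of the two definitions, followed by an illustration of size.

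**1. Who differs between the definitions**

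| Scheduled patient | Section 4 | Section 6 |
|---|---|---|
| Attended within the window, no event | in | in |
| Attended within the window, event before or after the visit | in, event | in, event |
| Never attended within the window, event | in, event | out |
| Never attended within the window, recovered | in, no event | out |

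Only the last two rows differ. A patient admitted, discharged and then seen in the unit within the window stays in under both.

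**2. Inputs**

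- n = visitors. Section 3 gives 64 consultations; with at least one consultation per visitor, n is at most 64. Smaller values of n are assumed.
- e = events among visitors, m = scheduled non-attenders, k = events among those non-attenders. All three are assumed; the protocol gives none.

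**3. Formula**

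Change in rate when non-attenders are added back:

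(e + k)/(n + m) − e/n = (nk − em)/[n(n + m)]

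This is positive only if k/m > e/n, that is, if events are proportionally more frequent among non-attenders than among visitors.

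**4. One non-attender (m = 1)**

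With an event (k = 1) the change is (n − e)/[n(n + 1)]. Recovered (k = 0) it is −e/[n(n + 1)]. In percentage points:

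| n | e | one missed event | one missed recovered patient |
|---|---|---|---|
| 64 | 0 | +1.54 | 0.00 |
| 64 | 3 | +1.47 | −0.07 |
| 64 | 6 | +1.39 | −0.14 |
| 40 | 0 | +2.44 | 0.00 |
| 40 | 3 | +2.26 | −0.18 |
| 40 | 6 | +2.07 | −0.37 |

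For example, n = 64 and e = 6 gives 58/(64 × 65) = 58/4160 = 1.39 points. Over n from 7 to 64 and e from 0 to 6, the one-event change is smallest at n = 64 for each e. The n = 64 rows are therefore minimum effects of a single missed event.

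**5. Several non-attenders (n = 64, e = 3, visitor rate 3/64 = 4.69%)**

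| m | k | rate | change (points) |
|---|---|---|---|
| 5 | 1 | 4/69 = 5.80% | +1.11 |
| 5 | 0 | 3/69 = 4.35% | −0.34 |
| 10 | 2 | 5/74 = 6.76% | +2.07 |
| 10 | 0 | 3/74 = 4.05% | −0.63 |

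The total effect has no upper limit that can be derived from the protocol, because m is not given.

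**The case against.** The best defence is that Section 4 is the operative eligibility rule and Section 6 only explains where the data came from in order to discuss consent. On that reading non-attenders are in and Section 6 is loosely worded. This may be what the authors meant. But Section 6 speaks of all data, and Section 3 independently ties the form and the late contact to consultation patients, so the text does not settle it.

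It can also be said that handling of non-attenders may be left to a statistical analysis plan. That is right, and silence on it is not the point here. The point is that the protocol states two populations that do not agree.

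The means to include non-attenders may already exist. The DPI, RedCap and the unified HUG database are named. Covicare's regular calls are not described as limited to visitors. Consent is described as sought by telephone at diagnosis, with posters at the emergency sites. This stands, and it makes the correction easy; it does not say that these sources will be used for non-attenders.

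Two stronger inferences are tempting and should not be drawn. A reader might conclude from the 5-of-7-day opening that a gap before the first visit is built in; it shows only that a gap is possible for some patients. A reader might also conclude that any event before the first visit is lost; only patients who never attend within the window are.

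Finally, Section 4 is itself limited to follow-up in HUG, while the introduction also allows follow-up by telephone or by the primary care physician. Adopting Section 4 therefore covers only part of the emergency decision.

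**Conclusion.** The conflict between Sections 4 and 6 is real, stands in current text and reaches the primary outcome. It is worth resolving before data are extracted.

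Its effect is conditional. If every scheduled patient attended within the window, the two cohorts coincide and nothing changes. The documents do not show that any non-attender exists.

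A reader might infer that selection by attendance must make the strategy look safer than it was. The documents do not support that, because recovered non-attenders are omitted as well and act in the other direction. The rate is understated only if k/m exceeds e/n, and neither proportion is given.

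As an illustration, with at most 64 visitors (and at least 7) and 0 to 6 assumed events among them, a single missed event changes the rate by at least about 1.4 to 1.5 points. A single missed recovered patient changes it by at most 0.14 points at 64 visitors.

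**What to change.** - Make the Section 4 population the analysis set, listed from emergency and DPI records whether or not the patient attended, and reword Section 6 to match.
- Take the primary outcome for every listed patient from the DPI, RedCap and the unified HUG database.
- Report the numbers scheduled, attended, and with an event before any visit.
- State which event the April 2 to May 5 window dates, so that it fits the chosen population. The choice of event is for the team.
- If only visitors can be included, label the result as applying to patients who reached the unit and report how many scheduled patients did not attend.

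The cost is a record query for a small cohort, some rewording, and a check that the existing consent route covers patients who never attended. Section 8 may require notice to the ethics committee beforehand. The reported rate may become slightly less favourable.
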